7. STATISTICAL METHODS

Statistical Analysis Plan (SAP)

There will be a formal SAP, separate from this Trial protocol. A formal SAP will be completed prior to database lock and the analysis of any Trial endpoints data. The SAP will detail the planned statistical analyses. The subsections below summarize the planned analyses.

Primary Outcome Endpoint

The primary outcome endpoint is to determine if the use of a protocolized strategy using advanced hemodynamic monitoring with Hypotension Prediction Index (HPI) software guidance for intraoperative hemodynamic management reduces postoperative complication rate in moderate- to high-risk non-cardiac surgery. The composite includes MACE (myocardial injury, stroke, non-fatal cardiac arrest, and death), AKI, and serious infections (pneumonia, deep and organ space surgical site infections, and sepsis).

THIS DOCUMENT CONTAINS CONFIDENTIAL AND PROPRIETARY INFORMATION OF EDWARDS LIFESCIENCES, LLC. IT MAY NOT BE REPRODUCED OR DISCLOSED WITHOUT PRIOR WRITTEN PERMISSION FROM EDWARDS LIFESCIENCES, LLC.
Edwards Lifesciences, Edwards, the stylized E logo, HemoSphere, Acumen, Acumen IQ, FloTrac, and ForeSight Elite oximetry Sensor are trademarks of Edwards Lifesciences Corporation.

Sample Size Justification

The goal of this study is to assess if the use of Hypotension Prediction Index (HPI) software guidance impacts the incidence of postoperative morbidity and mortality in the adult population undergoing moderate-to-high-risk noncardiac surgery (with a pressure monitoring with an arterial line). A relative reduction in the composite outcome within the treatment arm is expected. For a group sequential analysis, following the O'Brien and Fleming methodology, a sample size was calculated for a two-sample comparison of rates (two-sided). The hypothesis are as follows:

$$H_0: p_0 - p_1 \geq 0$$

$$H_1: p_0 \neq p_1$$

Assuming at least a 25% relative change in rate for the treatment (p_1) arm, a type I error (0.05), a power of 80%, and a reference rate of 0.31 (p_0) based on a meta-analysis^{6,10,14}, a sample size of 1426 subjects are needed. An additional 60 subjects may be included as roll-ins, which results in a total enrollment potential of 1486 subjects.

Analysis Populations

Modified Intent-to-treat (mITT)

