Assuming a power of 80% and a relative reduction of at least 25% in the composite score (reference proportion=0.31) with three total looks (two interim analysis, one final), the critical values for each time point were chosen to preserve an overall type-1 error rate of 0.05. The O'Brien and Fleming methodology was used to determine the boundary rule for deciding when to stop the trial prematurely. Futility was included. A relative reduction in the composite outcome within the treatment arm is expected. The alpha at each interim and the maximum number of observations are chosen so that the overall significance level is the probability of detecting the treatment difference under the null hypothesis. The table below shows the critical values:

Analysis	Information Rate	Effectiveness Boundary z-value (Upper, Lower)	Futility Boundary z-value (Upper, Lower)
First Interim Analysis	50%	(2.96259, -2.96259)	(0.40273, -0.40273)
Second Interim	75%	(2.35898, -2.35898)	(1.12741, -1.12741)
Final Analysis	100%	(2.01404, -2.01404)	(2.01404, -2.01404)

THIS DOCUMENT CONTAINS CONFIDENTIAL AND PROPRIETARY INFORMATION OF EDWARDS LIFESCIENCES, LLC. IT MAY NOT BE REPRODUCED OR DISCLOSED WITHOUT PRIOR WRITTEN PERMISSION FROM EDWARDS LIFESCIENCES, LLC.

Edwards Lifesciences, Edwards, the stylized E logo, HemoSphere, Acumen, Acumen IQ, FloTrac, and ForeSight Elite oximetry Sensor are trademarks of Edwards Lifesciences Corporation.

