An adapted group sequential design will be utilized for this clinical study, and to determine stopping rules, or to re-estimate the sample size by interim analysis outcomes ^[10, 12, 14, 17]. Adapted group sequential study design allows for one or more planned interim analyses when a prespecified stopping criteria is chosen. If the first interim analysis outcomes provide evidence for the necessity to enroll more patients, study sample size will be reassessed to determine the new appropriate sample size ^[1,10]. When there is sufficient evidence from study data collected at present stage in addition to the data collected from previous study stage, the clinical trial could be stopped early for already achieving the study objectives. A type I error (α) spending function will be used to design stopping boundaries for effectiveness, while allowing flexibility in how many interim analyses are designed, and at what time point they are conducted ^[4]. The methodology from O'Brien, Harrington, and Fleming ^[16] will be used to determine the effectiveness stopping criteria for prespecified first interim analysis, the secondary interim analysis, and the final analysis with 50%, 75%, and 100% information respectively. Many literatures proposed different methodologies from weighted combining test statistics to weighted combining p value from interim analyses to preserve type I error (α). The O'Brien-Fleming methodology, the conservative approach, spend little type I error (α) at the time of interim analyses and lead to boundary values at the final stage that

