are close to those from fixed sample designs,¹⁶¹ The O'Brien-Fleming formulae (to preserve the familywise error rate, a) is denoted as follows, $\text{PH}_0(|Z_1| < c_1, \dots, |Z_k| < c_k) = a$, where $c_i = \text{cp}(K, a)$, where c_i represents the positive critical values corresponding to stopping boundaries and the trial stops at an interim-i where $|Z_i| \geq c_i$. In this clinical trial, the O'Brien-Fleming methodology will be used to split the type I error (a) for each interim analysis, and also used to calculate critical value to judge if receives or rejects the null hypothesis. If the Z-statistic is close to the critical boundary value but the null hypothesis could not be rejected. By adapted group sequential study design principles, the study sample size will be re-assessed for the purpose to achieve the study objective by a third-party, independent, un-blinded statistician who will not unblind the study statistician and hence does not involve an alpha penalty. It is noted that a group sequential design with one(50%) interim analysis can reduce the expected sample size of a clinical trial by roughly 15%^{13, 11, 171}.

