 Edwards	Revision Date: May 11, 2022		Rev	A	For Use Only by Affiliates of Edwards Lifesciences	Page 6 of 19
	Title	Statistical Analysis Plan for HP/ SMART-BP Trial				

estimation, and is supported by the integrated evidence from physician clinical experience, scientific publications, and previous clinical trial results.

The hypothesis setting for this study used in sample size estimation is:

$H_0: P_1 \geq P_0$

$H_1: P_1 < P_0$

where p_1 and p_0 are the proportions of composite endpoint in treatment arm and control arm, respectively.

Moreover, two interim analyses will be designed at 50% and 75% subject enrollment with 30-day follow-up data, to assess the composite endpoint (pooled event rate) between treatment and control arms. To determine when the trial can be stopped prematurely for effectiveness, the O'Brien-Fleming methodology¹⁶ was used to determine the stopping boundary (alpha spending function). The O'Brien-Fleming methodology preserves the overall type I error across all interim analyses¹⁶. The overall type I error used for this one tail hypothesis test study is 0.025. If the Z-statistics is close to boundary value but could not reject null hypothesis, possibly the study sample size will be reassessed for the purpose to achieve study objective.

With these trial parameter and hypothesis settings, and two designed interim analyses plus a final analysis, 1486 subjects (including 15% attrition, including a maximum of 60 roll-ins) are needed for this clinical trial. The sample size is estimated with PASS2021. The critical Z value and the corresponding p value for effectiveness boundary are displayed in the following table for interim analysis and final analysis. By the study objective and experiment design, in effectiveness analysis if the Z value calculated by the data available at each study stage (interim analysis and final analysis) is less or equal the critical Z value listed in effectiveness boundary column, the null hypothesis will be rejected, and the study stops for the study objective is achieved. To simplify the interim analysis decision making procedure, the lower limit of the reference arm accumulated subjects with complication, and the upper limit of treatment arm accumulated subjects with complication are designed by the study design parameters, the study arm accumulated sample size at each analysis stage, and effectiveness boundary (critical Z value) estimated by O'Brien-Fleming methodology.

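### Protocol sets futility bounds at both interims, the SAP has none and declares no change; the SAP's definition of Z also contradicts its own rejection rule

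*Combined protocol and SAP*

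**What the plan says.** **Futility.** Protocol section 7, Planned Interim Analyses, has a boundary rule for "deciding when to stop the trial prematurely. Futility was included". Its table carries a column headed "Futility Boundary z-value (Upper, Lower") with ±0.40273 at the first interim and ±1.12741 at the second, beside effectiveness bounds of ±2.96259, ±2.35898 and ±2.01404. It does not say whether the futility bounds are binding.

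SAP 2.2 says that a spending function "will be used to design stopping boundaries for effectiveness, while allowing flexibility in how many interim analyses are designed". SAP 2.3 gives the purpose as "To determine when the trial can be stopped prematurely for effectiveness", and its table has an effectiveness column only. The interim steps in SAP 8.1 are to stop for effectiveness or, if Z is close to the bound, to continue with sample-size re-assessment. SAP section 10 states that nothing differs from the protocol-specified analyses.

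**Sidedness.** Under Sample Size Justification the protocol says "a sample size was calculated for a two-sample comparison of rates (two-sided"), with overall error 0.05. SAP 2.3 says: "The overall type I error used for this one tail hypothesis test study is 0.025".

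**Sign.** SAP 8.1 puts the reference-arm proportion minus the treatment-arm proportion in the numerator of Z. SAP 2.3 rejects if Z "is less or equal the critical Z value listed in effectiveness boundary column", where the listed values are -2.96259, -2.35898 and -2.01404; SAP 8.1 repeats the rule. SAP 2.2 gives a third form: c "represents the positive critical values corresponding to stopping boundaries and the trial stops at an interim-i where" the absolute value of Z is at least c.

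**Who acts.** Protocol section 10 confines DSMB recommendations on continuing or ending the trial to safety, but Stopping Rules in the same section lists interim results as a ground for stopping. SAP 6.1 has the DSMB evaluate interim data and gives no effectiveness or futility remit.

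**The concern.** Two current documents treat the same interim result differently. A Z near zero at 50% information falls inside the protocol's futility band. The SAP has no bound there and no instruction to stop, so continuation is the default. That decides whether a trial with no effect ends early or enrols almost in full, and the choice would have to be made by people who have already seen the result.

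The sign problem is separate and lies in the primary decision rule. Applied literally, the rule cannot declare the benefit the trial is designed to find, and it would declare success if the treatment did enough harm.

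**Working it through.** **Inputs.** Control rate 0.31, 25% relative reduction (treatment rate 0.31 × 0.75 = 0.2325) and 1,426 subjects, i.e. 713 per arm (protocol section 7). Looks at 50%, 75% and 100% information (both documents). Bounds as printed. As a sensitivity case, 606 evaluable per arm (0.85 × 713), which applies the SAP's 15% attrition as an assumption.

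**1. The plan's own bounds.** An O'Brien-Fleming-type spending function with one-sided alpha 0.025 and no futility bound gives 2.96259, 2.35901 and 2.01408, with nominal p of 0.00153, 0.00916 and 0.02200. This reproduces SAP 2.3. The effectiveness bounds spend the full alpha without credit for futility, so omitting futility does not inflate type I error. The protocol's two-sided 0.05 thresholds are the same size, so sidedness matters only for the form of the futility rule and for the harm side.

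**2. No true effect.** Three-look recursive integration, with the printed symmetric band always followed:

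- Futility stop at look 1: P(|Z| ≤ 0.40273) = 0.313. At look 2: 0.447. Total 0.76. Under the SAP: 0.
- All early stops, including effectiveness: 0.3159 and 0.4636.
- Expected N = 1,426 × (1 − 0.5 × 0.3159 − 0.25 × 0.4636) = 1,426 × 0.7262, about 1,036. Under the SAP's one-sided effectiveness rule it is 1,422.
- Two-sided type I error is 0.050 without futility and 0.047 with the band.
- Follow-up lag: 1,426/36 = 40 to 1,426/24 = 59 patients per month, if accrual is even over 24 to 36 months without a pause. Adding 40 to 60 patients × 0.7795 (the chance of an early stop) gives 1,067 to 1,082, against 1,422 to 1,423 under the SAP.
- If the bounds are used in the benefit direction only, 88% stop for futility and expected N before lag is about 874.

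**3. Design effect.** Drift at full information = 0.0775 / √[(0.31 × 0.69 + 0.2325 × 0.7675)/713] = 3.30.

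| Evaluable per arm | Futility stops with band | Power with band | Power, effectiveness only (sign aligned) |
|---|---|---|---|
| 713 | 5.2% | 0.892 | 0.906 |
| 606 | 7.9% | 0.838 | 0.855 |

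**4. Sign.** The SAP 2.3 event limits go into the SAP 8.1 formula, Z = (p0 − p1) / √[p0(1 − p0)/n + p1(1 − p1)/n]:

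| Look | n per arm | Events, control / treatment | p0 − p1 | SE | Z | SAP rejects if |
|---|---|---|---|---|---|---|
| 1 | 356.5 | 111 / 74 | 0.3114 − 0.2076 | 0.0326 | +3.18 | Z ≤ -2.96259 |
| 2 | 534.75 | 167 / 131 | 0.3123 − 0.2450 | 0.0273 | +2.46 | Z ≤ -2.35898 |
| 3 | 713 | 222 / 186 | 0.3114 − 0.2609 | 0.0239 | +2.11 | Z ≤ -2.01404 |

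None of the SAP's own success cases passes its written rule, whereas the absolute-value form in SAP 2.2 would stop at the first two. At the design effect the literal rule rejects with probability about 2 in 10 million (713 per arm). If treatment raised the rate by 25% (to 0.3875), it would reject with probability 0.86.

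**The case against.** First, SAP 8.1 says nothing about a Z near zero: it prescribes continuing only when Z is close to the critical value. Since SAP section 10 declares no changes, the protocol's futility bounds could be read as still in force. On that reading the SAP has an omission, not a contradiction, and the contrast of 76% with none falls away. The reading is possible, but it has to be inferred, and the SAP is the document meant to give the detail. The bounds would still lack a binding status and a direction, so the fix is the same.

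Second, the sign is probably a slip. The alternative hypothesis in SAP 2.3 and the event limits both show that fewer treatment-arm events is the aim, and a competent analyst would see it. This stands: the probability under the literal rule describes the text, not a likely course of events. The text still needs correcting.

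Third, the no-effect figures depend on how the bounds are used (76% or 88% futility stops), and sample-size re-assessment is not modelled. This also stands, and the verdict is conditioned on it.

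Fourth, the DSMB gap is narrower than it may look. Protocol section 4 gives the interim analysis to an unblinded independent biostatistician, SAP 2.2 gives re-assessment to a third-party statistician, protocol section 10 refers to a DSMB manual that is not among the documents, and section 20 lets the sponsor terminate. What stays open is who recommends an effectiveness or futility stop.

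**Conclusion.** Both contradictions hold and should be fixed.

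- **Futility.** With 713 per arm, no true effect and the symmetric band always followed, 76% of trials would stop for futility against none under the SAP as written. Expected size differs by 1,422 − 1,036 = 386 patients before follow-up lag. Benefit-direction use would widen the gap. At the design effect the band costs 1.3 points of power (1.6 at 606 per arm). These figures exclude safety stops and sample-size re-assessment. Type I error is not inflated, and safety stopping (protocol sections 10 and 20) is unaffected.
- **Sign.** Read literally, the SAP's primary rule would not declare benefit even when its own success limits are met. The intended direction is clear, so this is an error of drafting rather than of design, but it is in the rule that the unblinded statistician will apply.

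**What to change.** Before the first interim:

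1. Make the sign consistent in the SAP. Either define Z in 8.1 as treatment minus control, or make the bounds in 2.3 and 8.1 positive with rejection at or above them. Align the absolute-value form in 2.2.
2. State one sidedness in both documents.
3. Either carry the protocol's futility bounds into SAP 2.3 and 8.1, saying whether they are binding and whether they form a symmetric band or apply in the benefit direction only, or delete futility from protocol section 7. The symmetric band can be copied under either sign; a benefit-direction rule must follow the sign chosen in step 1.
4. Correct SAP section 10 to list the differences from the protocol.
5. Reconcile protocol section 10 with SAP 6.1, so that the DSMB's remit covers interim effectiveness results and any futility results.

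The cost is wording in both documents. If futility is kept and followed, it also costs about 1.3 points of power at 713 per arm (1.6 at 606); if it is deleted, no power is lost.

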THIS DOCUMENT CONTAINS CONFIDENTIAL AND PROPRIETARY INFORMATION OF EDWARDS LIFESCIENCES, LLC. IT MAY NOT BE REPRODUCED OR DISCLOSED WITHOUT PRIOR WRITTEN PERMISSION FROM EDWARDS LIFESCIENCES, LLC.
Edwards Lifesciences, Edwards, the stylized E logo, HemoSphere, Acumen, Acumen IQ, FloTrac, and ForeSight Elite oximetry Sensor are trademarks of Edwards Lifesciences Corporation.

Risk Management

The HemoSphere advanced monitoring platform, Acumen IQ sensor, FloTrac sensor, ForeSight Elite oximetry sensor and Hypotension Prediction Index (HPI) Feature Software have been tested to an established regimen of safety and performance testing (as applicable) required prior to use in human subjects in these clinical studies. This regimen includes requirements under applicable standards and regulations for packaging, shelf life, biocompatibility, microbiology, chemistry, sterility, electrical, mechanical and fatigue testing.

The indications and intended use of the HemoSphere advanced monitoring platform with Acumen™ Hypotension Prediction Index (HPI) feature software and Acumen IQ sensor remain unchanged from those previously cleared by FDA.

Table 3: Trial Devices and Indication for use

Device	Indication for use
HemoSphere Advance Monitoring Platform with Acumen Hypotension Prediction Index	The Acumen HPI feature software is intended for use in surgical or non-surgical patients receiving advanced hemodynamic monitoring. The Acumen HPI feature is considered to be additional quantitative information regarding the patient's physiological condition for reference only and no therapeutic decisions should be made based solely on the Acumen Hypotension Prediction Index (HPI) parameter.
Acumen IQ Sensor	The Acumen IQ sensor is indicated for use in intravascular pressure monitoring. It is also indicated for use with the Edwards arterial pressure based cardiac output monitoring devices or hardware to measure cardiac output.
FloTrac Sensor	The FloTrac sensor is indicated for use in intravascular pressure monitoring. It is also indicated for use with the Edwards arterial pressure based cardiac output monitoring devices or hardware to measure cardiac output. The FloTrac Sensors are cleared for use with the HemoSphere Advanced Monitor with HemoSphere Pressure Cable.
ForeSight Elite oximetry Sensor	The large ForeSight Elite oximetry Sensor is indicated for monitoring of absolute regional hemoglobin oxygen saturation of blood under the sensor in individuals at risk for reduced flow or no-flow ischemic states. It is intended for use on adults and transitional adolescents ≥ 40 kg.

Benefits

There are no guaranteed benefits to Trial participation. However, this will be the first prospective, multicenter, interventional, randomized controlled Trial that will highlight the potential effect the Hypotension Prediction Index (HPI) plus a treatment protocol has on morbidity and mortality.

THIS DOCUMENT CONTAINS CONFIDENTIAL AND PROPRIETARY INFORMATION OF EDWARDS LIFESCIENCES, LLC. IT MAY NOT BE REPRODUCED OR DISCLOSED WITHOUT PRIOR WRITTEN PERMISSION FROM EDWARDS LIFESCIENCES, LLC.

Edwards Lifesciences, Edwards, the stylized E logo, HemoSphere, Acumen, Acumen IQ, FloTrac, and ForeSight Elite oximetry Sensor are trademarks of Edwards Lifesciences Corporation.

9. REPORTABLE EVENTS

Recording and Reporting of Adverse Events

The Investigator and/or Designee(s) will determine whether any adverse events (AEs) have occurred. An AE is defined as any untoward medical occurrence in a clinical Trial of a Trial Device regardless of the causal relationship of the problem with the device or, if applicable, other Trial treatment or diagnostic product(s). Information for AEs with the Trial devices will be collected from the time a subject begins the Trial related procedure and/or is exposed to Trial product(s). AEs will also be collected during surgical intervention, post intervention, discharge and through the follow-up. AEs may be volunteered by subjects, clinicians, elicited from questioning by Investigator and/or Designee(s), or collected via observation. When a device or Trial related AE is suspected all available event information and will be provided to the Clinical Events Committee.

Once an AE/SAE/UADE is confirmed as such, event, date of onset, severity, duration, treatment (if required), resolution (or ongoing), assessment of seriousness, relationship to Trial procedure and relationship to device will be recorded on the appropriate eCRF or SAE Report Form and submitted as necessary by the Investigator and/or Designee(s). Any suspected AEs related to the Trial Device or Trial procedure must be reported to the Sponsor or Designee within 24 hours of first awareness of the event.

Severity of an AE

The following guidelines will be used to describe the severity of the AE:

- Mild – Event requires minimal or no treatment and do not interfere with the subject's daily activities.
- Moderate – Event results in a low level of inconvenience or concern with the therapeutic measures. Moderate events may cause some interference with functioning.
- Severe – Event interrupts a subject's usual daily activity and may require systemic drug therapy or other intervention. Severe events are usually potentially life-threatening or incapacitating. Of note, the term "severe" does not necessarily equate to "serious."

Relationship of an AE

The evaluation of relatedness must consider etiologies such as natural history of the underlying disease, concurrent illness, concomitant therapy, Trial-related procedures, accidents, and other external factors. In a device Trial, the Trial product(s) must always be suspect.

Causality of relationship to the Trial product(s) will be judged by the Investigator who examines and evaluates the subject based on temporal relationship and his/her clinical judgment. Causality of relationship will also be reviewed by the Investigator, and independently by a Medical Reviewer, as follows:

THIS DOCUMENT CONTAINS CONFIDENTIAL AND PROPRIETARY INFORMATION OF EDWARDS LIFESCIENCES, LLC. IT MAY NOT BE REPRODUCED OR DISCLOSED WITHOUT PRIOR WRITTEN PERMISSION FROM EDWARDS LIFESCIENCES, LLC.

Edwards Lifesciences, Edwards, the stylized E logo, HemoSphere, Acumen, Acumen IQ, FloTrac, and ForeSight Elite oximetry Sensor are trademarks of Edwards Lifesciences Corporation.

Not related:

- An event is clearly not and cannot be related to the Trial product(s), and/or evidence exists that the event is definitely related to another etiology. Note: Reporting of these events to the Sponsor or designee within 5 working days of first awareness of the event is not required unless the event was related to the Investigational Device or Trial.

Possibly Related:

- There is some evidence to suggest a causal relationship may exist; however, the event could have been produced by another cause (e.g., treatment, condition). Note: Reporting of these events to the Sponsor or designee within 5 working days of first awareness of the event is required.

Related:

- A relationship can be directly attributed to the use of the Investigational Device. Note: Reporting of these events to the Sponsor or designee within 24 hours of first awareness of the event is required.

Recording and Reporting of Adverse Device Effects

An adverse device effect (ADE) is defined as an AE related to the use of a Trial medical device. This definition includes AEs resulting from insufficient or inadequate instructions for use, deployment, implantation, installation or operation, or any malfunction of the investigation device. It also includes any AE resulting from use error or from intentional misuse of the Trial Device.

ADEs must be reported to the Sponsor or designee, within 24 hours of first awareness of the event. Notification should be done via email, fax, telephone, or direct communication followed by direct entry of AE/SAE data into the eCRF. In addition, the Trial site will report confirmed ADEs related to their IRB in accordance with the IRB's/IEC's requirements. ADEs will also be reported to the FDA, as required.

Recording and Reporting of Serious Adverse Event

A serious adverse event (SAE) is defined as an AE that results in any of the following outcomes: death, a life-threatening adverse event, inpatient hospitalization, or prolongation of existing hospitalization, a persistent or significant disability/incapacity, or a congenital anomaly/birth defect.

Recording and Reporting of Serious Adverse Device Effects

A serious adverse device effect (SADE) is an ADE that has resulted in any of the consequences or characteristics of a SAE.

SADEs must be reported to the Sponsor or designee, within 24 hours of first awareness of the event. Notification should be done via email, fax, telephone, or direct communication followed by direct entry of AE/SAE data into the eCRF. In addition, the Trial site will report confirmed SADEs to their IRB in accordance with the IRB's/IEC's requirements. SADEs will also be reported to the FDA, as required.

THIS DOCUMENT CONTAINS CONFIDENTIAL AND PROPRIETARY INFORMATION OF EDWARDS LIFESCIENCES, LLC. IT MAY NOT BE REPRODUCED OR DISCLOSED WITHOUT PRIOR WRITTEN PERMISSION FROM EDWARDS LIFESCIENCES, LLC.

Edwards Lifesciences, Edwards, the stylized E logo, HemoSphere, Acumen, Acumen IQ, FloTrac, and ForeSight Elite oximetry Sensor are trademarks of Edwards Lifesciences Corporation.

Recording and Reporting of Unanticipated Adverse Device Events

Unanticipated adverse device effect (UADE) is defined in 21 CFR 812.3(s) as any serious adverse effect on health or safety or any life-threatening problem or death caused by, or associated with, a device, if that effect, problem, or death was not previously identified in nature, severity, or degree of incidence in the investigational plan or application (including supplementary plan or application), or any other unanticipated serious problem associated with a device that relates to the rights, safety, or welfare of subjects. In contrast, an anticipated adverse device effect is an effect which by its nature, incidence, severity, or outcome has been identified in the risk analysis report.

UADEs must be reported to the Sponsor or designee within 24 hours and submitted to the reviewing IRB as soon as possible, but in no event later than 10 working days after the Investigator first learns of the effect.

All AEs related to the Trial Device or Trial will be reviewed by the Investigator and/or Designee(s) and Sponsor. These AEs will be followed until they are adequately resolved, explained by the Investigator and/or Designee(s), until subject has completed follow-up, terminated the Trial early, is lost to follow-up or has been withdrawn from the Trial.

Recording and Reporting of Deaths

Events resulting in death during the subject's enrollment in this Trial are not expected to occur as a result of participation in the Trial. In the event of subject death, every reasonable effort should be made to obtain a copy of the autopsy report and/or death summary. Information on the date and cause of death and its relationship to the Trial device will be determined by the Investigator and/or Designee and recorded on the appropriate AE eCRF and submitted on an SAE Report Form as necessary.

Recording and Reporting of Adverse Events Associated with Commercial Components

Any adverse event associated with an FDA cleared component will be recorded as a device complaint and reported via the MDR program (21 CFR Part 803). Complaints will also be reported to the IRB in accordance with each IRB's/IEC's requirements. Device complaints should be reported to the Sponsor as soon as the site becomes aware of the complaint. The Sponsor may request further information and documentation from the site when complications and/or malfunctions are observed and reported.

THIS DOCUMENT CONTAINS CONFIDENTIAL AND PROPRIETARY INFORMATION OF EDWARDS LIFESCIENCES, LLC. IT MAY NOT BE REPRODUCED OR DISCLOSED WITHOUT PRIOR WRITTEN PERMISSION FROM EDWARDS LIFESCIENCES, LLC.

Edwards Lifesciences, Edwards, the stylized E logo, HemoSphere, Acumen, Acumen IQ, FloTrac, and ForeSight Elite oximetry Sensor are trademarks of Edwards Lifesciences Corporation.

Recording and Reporting of Pre-Existing Conditions

Pre-existing medical conditions and symptoms due to pre-existing medical conditions, surgery or admission to ICU will not be recorded as adverse events. The admission of a critically ill patient in the intensive care unit is commonly due to one or several serious medical conditions and/or a major surgery, which may cause changes and abnormalities of blood chemistry, diagnostic and physiological parameters. In the event there is a deterioration of a pre-existing medical condition or symptoms due to the use of the Trial product(s) or a Trial related procedure, then the review of the event will be initiated, and an AE will be recorded if it meets the definition. Any events occurring prior to the exposure to the Trial product(s) or Trial related procedure will be recorded as medical history.

Reporting Adverse Events to the FDA

Confirmed UADEs will be evaluated by the Medical Reviewer. The FDA, all participating principal investigators, and their reviewing IRBs/IECs will be informed no later than 10 working days after Edwards Lifesciences or designee first becomes aware of the effect.

Reporting Adverse Events to the Responsible IRB

In accordance with applicable policies of the IRB, the Investigator will report, any observed or volunteered confirmed adverse event that is determined to be (1) unexpected; (2) related or possibly related to the research; and/or (3) involves increased or greater risk of harm to participant(s) or others than was previously known or approved by the IRB. AE reports will be submitted to the IRB in accordance with the IRB policies and procedures.

Confirmed UADEs will be evaluated, and the reviewing IRB will be informed of the results of the Trial no later than 10 working days after Edwards or when the designee first becomes aware of the effect.

Recording and Reporting AE Time Period

At each Trial visit, the Investigator and/or Designee(s) will inquire about the occurrence of AE/SAEs/ADEs/SADEs/UADEs since the last visit. AE/SAEs/ADEs/SADEs/UADEs will be followed until they are adequately resolved, explained by the Investigator and/or Designee(s), until subject has completed follow-up, terminated the Trial early, is lost to follow-up or has been withdrawn from the Trial.

THIS DOCUMENT CONTAINS CONFIDENTIAL AND PROPRIETARY INFORMATION OF EDWARDS LIFESCIENCES, LLC. IT MAY NOT BE REPRODUCED OR DISCLOSED WITHOUT PRIOR WRITTEN PERMISSION FROM EDWARDS LIFESCIENCES, LLC.

